8.1 Definitions

8.1.1 Adverse Outcome

Adverse outcome will be calculated according to the following rules:

- Death is defined using mortality status on the follow up form.
- Needing respiratory, cardiovascular or renal support is defined if any of the following have been recorded in the follow up admissions
 - Respiratory: mechanical ventilation, non-invasive ventilation, CPAP, HFNO;
 - Cardiovascular: ECMO, inotropic/vasopressor drugs, central venous pressure measurement, invasive intra-arterial blood pressure measurement;
 - Renal: haemofiltration, haemodialysis, peritoneal dialysis.

Any support recorded in 'other' (not flagged as the options above) are to be sent to the chief investigator and a clinical member of the PMG to manually review and categorise where appropriate.

8.2 CURB-65

The CURB-65 score uses five parameters, each scoring 1 point when positive and zero if negative, to give a total score between zero and five.

Five parameters:

- 1. Confusion: GCS-V is less than 4 or GCS total is less than 15 or AVPU is recorded as V, P or U
- 2. Urea: Raised blood urea nitrogen over 7mmol/litre
- 3. Respiratory: rate of 30 breaths per minute or more
- 4. Blood pressure: diastolic BP is 60mmHg or less or systolic BP is 90 mmHg or less
- 5. Age: 65 years or more

Missing data: The rules above effectively classify missing data as normal. Low rates of missing data are expected for all parameters except urea. The CRB-65 score [7] is recommended for community settings where access to blood testing is more limited. It is the same as CURB-65 but is a 4-point scale that does not include urea with the threshold remaining as <2 for low risk, 2+ for high risk. Therefore an alternative way of handling missing data for urea is to calculate the CRB-65 score. Further sensitivity analysis may be considered if physiological variables have missing rates > 5%. If a patient has fewer than three of the five parameters complete, the score will not be calculated.

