6.2 Existing triage tools

We will evaluate the following existing triage methods:

- CURB-65 [7]
- PMEWS [8]
- The Swine Flu Hospital Pathway [9]
- NEWS2 [10]

- The WHO decision-making algorithm for hospitalisation with pneumonia [11]
- POPS [12]
- COAST [13]

The triage tools will be retrospectively applied to the data by the study statisticians. CURB-65 and PMEWS will be evaluated in adults only, NEWS2 will be evaluated in adults excluding pregnant women, POPS will be evaluated in children only. Details of scoring and handling missing data for the triage tools are given in sections 8.2 to 8.5. Existing triage tools will be assessed by plotting the ROC curve and calculating the area under the ROC curve (c-statistic) for discriminating between cases with and without adverse outcome. Sensitivity, specificity, positive predictive value and negative predictive value at key decision making thresholds will be calculated and presented:

Tool	Threshold
CURB-65	0-1 versus 2-5
PMEWS	0-2 versus 3+
The Swine Flu Hospital Pathway	0 versus 1+
NEWS2	0-4 versus 5-20, 0-4 versus 50-20 or scoring at least
	3 in one category
WHO	0 versus 1
POPS	0-4 versus 5+
COAST	0-2 versus 3+

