6.5 External validation of prediction models and new triage tools

The population will be split into a development and validation cohort if at least 400 adverse outcomes are recorded (resulting in at least 200 events in each cohort). This will provide sufficient power for the triage tools to be validated [18]. We anticipate there will be insufficient events to split the child cohort and hence this population will not be split. The cohort will be split by date across certain sites. A table of characteristics for the development and validation cohort will be presented to show how the cohorts differ.

The final logistic regression models (both the initial assessment model and full model) will be externally validated by applying the predictive model and triage tools and assessing calibration, discrimination and net benefit in order to assess reproducibility. The validation cohort will also be used to compare the newly developed triage tools against the existing triage tool that performed the best in the development cohort (based on AUROC) by comparing AUROC for these tools.

In order to assess transportability of the new triage tools into different populations or settings, future cohorts must be used to examine heterogeneity in performance across different populations and settings.

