8.3 PMEWS

PMEWS uses six physiological parameters and patient parameters to calculate a score from zero to 19. The score is calculated by taking the score in the table below dependent on each of the six physiological parameters then adding points for two patient parameters after if they are positive.

Physiological:

Score	3	2	1	0	1	2	3
Respiratory Rate	≤8			9-18	19-25	26-29	≥30
SaO ₂	<89	90-93	94-96	>96			
Pulse Rate	≤40	41-50		51-100	101-110	111-129	≥130
Systolic BP	≤70	71-90	90-100	>100			
Temperature		≤35.0	35.1-36.0	36.1-37.9	38-38.9	≥39	
Neuro				Alert	Confused Agitated*	Voice	Pain Uncon

* confused/agitated will be defined based on GCS-V<4 or GCS total<15, or if confusion is ticked as a presenting feature

Patient:

- 1. Add 1 point if age>65
- 2. Add 1 point if either:
 - a. Patient lives alone / no fixed abode or
 - b. has a co-morbidity (respiratory, cardiac, renal, immunosuppressed, diabetes)
 - c. performance status is more than two suggesting limited activity can self-care, limited activity limited self-care, or bed/chair bound no self-care.

Missing data: If data is missing one or two variables then the normal score (zero) should be assumed. If more than three variables are missing the patient should be excluded. These rules effectively classify

missing data as normal. Low rates of missing data are expected for the physiological parameters and age. The remaining parameters only account for one point and therefore would be within the range of using the patient data. Sensitivity analysis will be considered if physiological variables have missing rates > 5%. If AVPU is missing and GCS is recorded, impute the following AVPU scores using GCS: 0 if GCS=15, 1 if GCS=12-14; 2 if GCS=9-11 and 3 if GCS<9.

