Missing data: As the measure only requires one score then missing data will be classified as normal. Low rates of missing data are expected for the physiological parameters however it will not be possible to determine whether failure to tick the relevant boxes represented missing data or not. The measure will not be calculated if fewer than three of the parameters are complete.

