8.6 The WHO decision-making algorithm for hospitalisation with pneumonia

The WHO decision making algorithm for hospitalisation with pneumonia suggests an adult patient is admitted (score 1) if any of the following are present:

• respiratory rate >30/minute,

- oxygen saturation <90%,
- respiratory distress,
- age >60,
- any of the following comorbidities; hypertension, diabetes, cardiovascular disease, chronic respiratory disease, renal impairment immunosuppression

A patient will score 0 otherwise. Any missing data will be assumed as normal. A score will not be calculated if fewer than three of the above are complete.

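### Adult triage tools code confusion differently from the same form and are scored on different adults, yet the comparator is chosen by ranking their AUROCs

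*SAP*

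**What the plan says.** **Confusion.** Section 6.3 lists confusion among the presenting features, so the form has a tick for it. The adult tools use it unevenly:

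- CURB-65 (8.2): "Confusion: GCS-V is less than 4 or GCS total is less than 15 or AVPU is recorded as V, P or U". The tick is not used.
- PMEWS (8.3): GCS criteria, "or if confusion is ticked as a presenting feature".
- Swine Flu pathway (8.4): item F names new confusion as an adult criterion, but the note under the table makes it positive only on GCS below 15 or AVPU other than A.
- NEWS2 (8.5): confusion scores 3 points, and no data field is named.

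**Who is scored.** Section 6.2 states: "CURB-65 and PMEWS will be evaluated in adults only, NEWS2 will be evaluated in adults excluding pregnant women". CURB-65 needs three of its five parameters and NEWS2 three of its seven. For the Swine Flu pathway, "The measure will not be calculated if fewer than three of the parameters are complete". For the adult WHO rule (8.6), "A score will not be calculated if fewer than three of the above are complete". PMEWS sets one or two missing variables to zero and excludes patients with more than three missing.

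**How the result is used.** If the cohort is split, section 6.5 compares the new tools "against the existing triage tool that performed the best in the development cohort", judged by AUROC. It does not say on which patients the existing tools are to be ranked.

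**The concern.** Choosing a comparator by the highest AUROC presumes that the AUROCs differ because the tools differ. Here part of any difference could come from two avoidable sources: whether an available field was used for the same clinical item, and which adults entered each calculation.

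The confusion gap matters most where one item decides the result. Under section 8.5, 3 points in a single NEWS2 category is high risk, so the unnamed field can settle the classification by itself. The Swine Flu pathway is positive on any one item. Its second score also counts other clinical concern as positive when any NEWS2 parameter scores 3, so it inherits the NEWS2 ambiguity.

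The tick is also a candidate predictor in both new models (6.3). A new tool could therefore use information that its comparator was denied by coding alone.

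**Working it through.** **1. One patient through the adult tools.** Take confusion ticked, AVPU recorded as A, and no GCS.

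| Tool | GCS or AVPU used | Tick used | Result for this item |
|---|---|---|---|
| CURB-65 (8.2) | yes | no | 0 |
| PMEWS (8.3) | yes | yes | 1 |
| Swine Flu item F (8.4) | yes | no | negative |
| NEWS2 (8.5) | field not named | not stated | 0 or 3 |
| WHO adult (8.6) | no such item | no such item | unaffected |

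**2. Who is scored.** Suppose only respiratory rate, SaO2 and pulse are measured, with age and comorbidity known.

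- NEWS2: 3 of 7 available, scored.
- CURB-65: 2 of 5 available (respiratory rate, age), not scored.
- PMEWS: 3 of 8 missing (systolic BP, temperature, neuro). Section 8.3 covers one or two missing and more than three missing, so the case is undefined.

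Eight measured items (respiratory rate, SaO2, pulse, BP, temperature, neuro, air/oxygen, urea) give 2^8 = 256 availability patterns. With age and comorbidity known:

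- all three tools score the patient in 82;
- none does in 37;
- they definitely disagree in 6 + 15 + 21 + 15 = 57;
- PMEWS is undefined in 80 (20 ways to miss three of its six physiological items, times 4 states of urea and air/oxygen).

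The sum is 82 + 37 + 57 + 80 = 256. These patterns are not weighted by how often they occur. They show that the rules diverge, not how often.

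**3. Scale: the SAP's own precision.** Section 2 gives standard errors for a c-statistic of 0.8. The formula sqrt(0.8 x 0.2 / events) gives 0.0327, 0.0358, 0.0400, 0.0462 and 0.0566 for 150, 125, 100, 75 and 50 events. The SAP has 0.033, 0.036, 0.040, 0.046 and 0.056, which agrees apart from rounding of the last.

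For a difference between two tools on the same patients, take section 2's correlation of 0.6 as that between the two AUROC estimates. Then SE(difference) = SE x sqrt(2 x (1 - 0.6)):

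- 150 events: 0.0327 x 0.894 = 0.029
- 200 events: 0.0283 x 0.894 = 0.025
- 400 events: 0.0200 x 0.894 = 0.018

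Section 6.5 splits the cohort at 400 or more events, giving at least 200 in the development half, so 0.025 is the upper end for the ranking step.

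**4. Pregnancy exclusion (assumed inputs).** Let f be the share of non-events who are pregnant and C the concordance of events against them, with AUROC 0.8 otherwise. Shift = f x (C - 0.8).

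- f = 0.5%, C = 0.85: 0.005 x 0.05 = 0.0002 (truncated)
- f = 5%, C = 0.95: 0.05 x 0.15 = 0.0075

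**5. Confusion tick (assumed inputs).** In an illustrative simulation, confusion points were added for ticked patients with normal GCS/AVPU. The simulated scores had AUROC 0.721 (CURB-65-like) and 0.765 (NEWS2-like) without the tick.

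| Ticked: events / non-events | CURB-65-like shift | NEWS2-like shift |
|---|---|---|
| 5% / 2% | +0.004 | +0.003 |
| 10% / 3% | +0.010 | +0.009 |
| 15% / 3% | +0.019 | +0.017 |
| 5% / 5% | -0.004 | -0.006 |
| 15% / 5% | +0.014 | +0.012 |

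The sign depends on how much commoner the tick is among events. The largest shift, 0.019, is smaller than the 0.025 standard error at 200 events but of the same order.

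**The case against.** The tools differ by design. The adult WHO rule has no confusion item, PMEWS has its own confused/agitated level, and whether a presenting-feature tick belongs in each instrument's neurological item is partly a mapping choice. A confused patient with a recorded GCS below 15 already scores on CURB-65. The pregnancy exclusion is stated openly. The SAP expects little missing physiology and considers sensitivity analyses above 5% missing for CURB-65, PMEWS and NEWS2. Section 7.1 also removes cases lacking more than half the model variables. Section 2 sizes the validation comparison with correlated scores, which implies that both scores exist in the same patients.

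Most of this stands, and it limits the size. It does not explain why the tick counts in one tool and not in others, name the NEWS2 field, or fix the patients for the ranking. The section 7.1 exclusion is common to all tools and does not equalise their separate rules.

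A reader might infer three stronger things that the SAP does not support:

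- **That patients without observations all enter the Swine Flu and WHO results as low risk.** WHO scores 1 on age over 60, a listed comorbidity or distress alone, and Swine Flu is positive on a ticked distress, exhaustion or dehydration box. Appendix 1 treats medical history as missing when the none box is also unticked. Section 7.1 cites that appendix for the prognostic models, not the existing tools, and section 8.4 says an unticked box cannot be told from missing data.
- **That Objective 1 itself ranks the tools.** It asks for the discriminant value of triage methods, and section 6.2 reports each tool separately. Ranking appears only in section 6.5.
- **That only measured observations should count towards the minimum of three.** The adult WHO rule has only two, respiratory rate and saturation, so it could never be scored and a common set including it would be empty.

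**Conclusion.** The concern holds in limited form. Confusion is derived inconsistently from one form, the NEWS2 source is undefined, PMEWS has no rule at exactly three missing variables, and the comparator is chosen by AUROC with no common set of patients.

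The size cannot be derived from the SAP. On the assumed inputs above, confusion coding moves AUROC by about -0.006 to +0.019 and the pregnancy exclusion by under 0.01. The minimum-data rules probably add little if missingness is as low as the SAP expects. A close ranking could therefore change and a wide one could not. The separate accuracy estimates in section 6.2 are not invalidated, though the NEWS2 figures, and those of the second Swine Flu score, cannot be reproduced until the confusion field is named.

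**What to change.** - In sections 8.2 to 8.5, apply one data rule for confusion in adults to CURB-65, PMEWS, NEWS2 and the Swine Flu pathway: GCS total below 15, or AVPU not A, or confusion ticked. Keep the separate Voice and Pain levels of PMEWS. If GCS-V is retained for patients without a total, retain it in all four.
- In section 6.5, select the comparator and compare AUROCs on the adults in whom all compared tools are scored (non-pregnant when NEWS2 is included). Report each tool on its own set as a secondary table.
- In section 8.3, state what happens when exactly three PMEWS variables are missing.
- Leave the three-item minimum rules otherwise as they are.

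The cost is SAP wording and a small amount of code. The head-to-head comparison loses slightly fewer than the full number of scorable patients would suggest only if missingness is low; the secondary table keeps every result now planned.

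### CRB-65 is offered as the alternative for missing urea in CURB-65, but it gives a urea-missing patient the same score, so the missing-as-normal assumption for urea goes unchecked

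*SAP*

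**What the plan says.** Section 8.2 of the SAP builds CURB-65 from confusion, urea, respiratory rate, blood pressure and age, "each scoring 1 point when positive and zero if negative". On missing data it states: "The rules above effectively classify missing data as normal". It adds: "Low rates of missing data are expected for all parameters except urea".

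For urea it then offers CRB-65: "an alternative way of handling missing data for urea is to calculate the CRB-65 score". CRB-65 is described as the same score on a four-point scale that "does not include urea with the threshold remaining as <2 for low risk, 2+ for high risk". Section 6.2 sets the CURB-65 cut at the same place, 0-1 against 2-5.

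Two further rules in section 8.2 matter here. One concerns completeness: "If a patient has fewer than three of the five parameters complete, the score will not be calculated". The other is the only further check mentioned for this tool: "Further sensitivity analysis may be considered if physiological variables have missing rates > 5" (the figure is a percentage).

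Elsewhere, section 7.1 refers missing data in the existing tools back to the tool sections, and section 7.1.1 confines multiple imputation to development of the prognostic model. Appendix 1 lists urea under Bloods, apart from Physiology.

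**The concern.** A second way of handling missing data is useful only if it can give a different answer from the first. Here the second way appears to be the first under another name, for exactly the patients concerned.

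Evaluating existing triage tools is objective 1 of the study (section 1.1). Section 6.5 also takes the existing tool with the best development-cohort AUROC as the comparator for the new tools, so the handling of urea bears on whether CURB-65 is chosen. Scoring an unmeasured urea as 0 can leave a patient's score unchanged or too low, never too high. Compared with the same cohort with urea fully measured, sensitivity at 2 or more can therefore only be equal or lower, and specificity equal or higher. The item most exposed to this assumption is the one for which the named alternative cannot show its effect.

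**Working it through.** There is no planned figure to reproduce. The check is of a scoring identity, using the SAP's own definitions.

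**Inputs**
- Each item scores 1 or 0, and a missing item scores 0 (section 8.2).
- CRB-65 is CURB-65 without urea (section 8.2).
- High risk is 2 or more for both scores (sections 6.2 and 8.2).
- At least three of the five items must be complete (section 8.2). The SAP sets no separate rule for CRB-65, so the same minimum of three is assumed.

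**Step 1: a patient with urea missing.** Write C, R, B and A for confusion, respiratory rate, blood pressure and age.
- Main rule: CURB-65 = C + 0 + R + B + A.
- Alternative: CRB-65 = C + R + B + A.

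The two are equal. Each of the four items can be 0, 1 or missing, giving 3 × 3 × 3 × 3 = 81 patterns. Of these, 16 (all four present) + 4 × 8 = 32 (exactly three present) = 48 can be scored. Enumerating all 81 gave 0 differences in score, 0 in class at 2 or more, and 0 in eligibility.

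**Step 2: CRB-65 substituted only where urea is missing.** No patient's score changes. AUROC, sensitivity, specificity and both predictive values are therefore unchanged.

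**Step 3: CRB-65 calculated for the whole cohort.** Take the 2 × 2 × 2 × 2 = 16 complete patterns of the other four items.
- Urea measured and not raised: 0 of 16 patterns change.
- Urea measured and above 7 mmol/litre: the score falls by 1 in all 16, and the class changes in the 4 where C + R + B + A = 1.
- Urea missing: no change, as in step 1.

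Cohort results can differ here, but only because measured values are discarded. The patients whose handling is in question are untouched.

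**Step 4: a contrast that can differ.** Score missing urea as abnormal, so that CURB-65 = C + 1 + R + B + A. Every urea-missing patient with C + R + B + A = 1 moves from low to high risk, which is 4 of the 16 complete patterns. The share of the cohort that moves is (share with urea missing) × (share of those with exactly one other point). The SAP gives neither share. A patient's score with urea measured must equal either the main-rule score or that score plus 1. For a given cohort, sensitivity and specificity at 2 or more therefore lie between the results of these two rules. The same bound does not hold for AUROC.

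**Step 5: other provisions that might cover urea.**
- The further analysis in section 8.2 is optional, has no stated method, and is triggered by physiological variables. Appendix 1 does not class urea as one.
- Section 7.1 sends the question back to the tool sections.
- Section 7.1.1 excludes the tools from multiple imputation.

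None of these supplies a check.

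**The case against.** The strongest reply is that section 8.2 does not restrict CRB-65 to urea-missing patients. It introduces CRB-65 as a recognised score for settings with limited blood testing, so scoring everyone with it is a plausible reading, and step 3 shows that cohort results could then differ. This stands. A reader might infer that the two sets of results must agree and that their agreement would pass for robustness. That follows only under substitution, and the SAP does not say which use is meant. The narrower point survives both readings: neither changes the score of a urea-missing patient.

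Second, scoring missing as normal is a reasoned choice. Section 7.1 says a test may be skipped because a normal result is expected, and several other tools in section 8 use the same rule. This also stands. It makes the assumption plausible but does not test it.

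Third, a reader might try to size the harm. Assume 10-50% of patients lack urea, 20-40% of those have exactly one other point, and 10-50% of those would have raised urea. Then 0.1 × 0.2 × 0.1 = 0.2% to 0.5 × 0.4 × 0.5 = 10% of patients would be classed low risk when a measured urea would make them high risk. The documents do not support this as an estimate. All three shares are assumed, the upper end sits badly with the reason for missingness in section 7.1, and a share of all patients does not translate into sensitivity, which depends only on those with an adverse outcome.

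Fourth, the consequence is limited: this is an optional alternative for one of seven existing tools, and the main CURB-65 rule is clear and reproducible. That is fair, and it limits the weight of the point.

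**Conclusion.** The point holds in a limited form. By the SAP's own definitions, CRB-65 is not an alternative treatment of missing urea: it gives the same score in all 81 patterns, and the same class at 2 or more. Substituted for urea-missing patients, it changes nothing. Applied to everyone, it is another tool and leaves the assumption untested. Urea, the one CURB-65 item not expected to have low missingness, therefore has no working sensitivity check.

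The identity rests only on the scoring rules and the shared threshold. Its equality on eligibility assumes the three-item minimum also applies to CRB-65. It extends to the three-level interpretation in section 8.9 only if the same levels were used for CRB-65, which the SAP does not state. The documents do not show that CURB-65 performance is materially distorted, and the size of any effect cannot be given without the urea missing rate. The point merits a correction to section 8.2 and does not call the main CURB-65 analysis into question.

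**What to change.** In section 8.2:
- State that CRB-65, if reported, is a separate tool scored for the whole cohort, and remove its description as a way of handling missing urea.
- Name as the missing-urea check the AUROC, sensitivity, specificity and predictive values of CURB-65 in patients with measured urea. Report the number and percentage with urea missing beside it. The drawback is that these patients are a clinically selected group if tests were skipped when expected to be normal, so a difference from the main result may reflect case mix as well as the scoring rule.
- Optionally, add CURB-65 with missing urea scored as abnormal. It is an extreme assumption, but together with the main rule it brackets sensitivity and specificity at the 2 or more cut.

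Multiply imputed urea may be added, but it is not available under the plan as written. Section 7.1.1 would have to be widened to the triage tools. Urea is also dropped from the predictive models if more than 50% is missing, so imputations may not exist when they are most needed. Appendix 1 imputes using the outcome as well, which would need justifying before imputed values are used to judge a tool's discrimination.

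The cost is SAP wording and one or two extra result rows. The measured-urea analysis and the bound need no new data.
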